7.7. Concomitant Therapy

Patients may continue to receive the background standard therapies for SLE they were receiving at completion of the originating study. Changes in dose of background standard therapies for SLE, such as an increase in dose of antimalarials or immunosuppressants, are permitted during the study. Initiation of new antimalarials or immunosuppressants are prohibited during the study.

In addition, changes in concomitant medication, such as an increase in corticosteroids to manage any increase in disease activity or corticosteroid tapering, are permitted during the study in accordance with long term management of disease activity and at the investigator's discretion. Any required corticosteroid bursts should be aligned with clinical practice.

Prohibited concomitant treatments include those outlined in the exclusion criteria of the originating trials.

- Scheduled parenteral corticosteroids, biologic treatments for immunologic disease, cyclophosphamide, belimumab, anifrolumab (or any other anti-IFN therapy), rituximab, any other B cell depleting therapies, intravenous immunoglobulin or any other JAK inhibitors.

Any changes to the patient's medication must be discussed with the investigator. Patients should be instructed to consult the investigator or other appropriate study personnel at the site before taking any new medications or supplements.

Additional medications are to be avoided during the study unless required to treat an AE or for the treatment of an ongoing medical problem.

Any additional medication, whether prescription or over-the-counter, used at baseline and/or during the course of the study must be documented in the eCRF with start and stop dates.

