### 6.4.2.3. Mixed Model for Repeated Measures

For continuous variables, an MMRM analysis with a missing at random assumption for handling missing data will be performed. This likelihood-based analysis takes into account both missingness of data and the correlation of the repeated measurements.

The MMRM method may be justified when the estimand of interest uses the hypothetical strategy (EMA2020) for handling intercurrent events. In this strategy, the scientific question of interest is to assess the effect of study treatment in a hypothetical trial where all patients have complete data and continue to take study treatment as directed without dropping out of the study.

For patients who have prohibited medication use any time after baseline, any observed data after the date of the prohibited medication use will be excluded from the MMRM analysis. The earliest date of prohibited medications will be used for censoring.

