## 6.10. Concomitant Therapy

Concomitant medications will be coded and descriptively summarized by treatment group in terms of frequencies and percentages using the mITT population.

Medications taken during JAİM that started before the last date of the treatment period and are ongoing or ended during the treatment period will be classified as "concomitant" medication.

The baseline for concomitant medications is defined as the medication and dose taken on the day prior to the date of the first dose of study drug administration (baricitinib).

For Zoster and tuberculosis (TB) vaccine, since only start date is reported, if start date is missing, these medications will be considered to be prior therapy.

Patients may continue to receive the background standard therapies for SLE they were receiving at completion of the originating study. Changes in dose of background standard therapies for SLE, such as an increase in dose of antimalarials or immunosuppressants, are permitted during the study. In addition, changes in concomitant medication, such as an increase in corticosteroids to manage any increase in disease activity or corticosteroid tapering, are permitted during the study in accordance with long term management of disease activity and at the investigator's discretion. Any required corticosteroid bursts should be aligned with clinical practice.

Prohibited concomitant medications are defined as

- initiation of new antimalarials or immunosuppressants
- recurrent intravenous injection of any corticosteroids, or
- having any other biologics or protocol-prohibited concomitant medications, defined from the ATC codes of L01XC, L01XX, L04AB, L04AC, V98, or J06B (excluding J06BB).

Prohibited medications during the treatment period will be reviewed by the study team to assess clinical significance of change in medication. The final determination of clinical meaningfulness will be documented and will be incorporated into the analysis datasets.

Concomitant medication use during Study JAIM will be summarized by treatment, organized according to ATC code level 1 and preferred name, sorted by frequency in the placebo to baricitinib 4-mg group. The summaries of concomitant medications will be provided overall and separately for concomitant medications used to treat SLE and for statin concomitant medications. Note that a patient will only be counted once, regardless of how many times medication included under the same preferred name was taken.

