### **6.10.1. Corticosteroid Dosing Conversion**

To allow for assessments of changes in doses of various corticosteroids, all corticosteroid doses will be standardized to an equivalent prednisone dose. [Appendix 1](#) provides a complete summary of conversion factors for each corticosteroid medication identified during the study, instructions for selecting corticosteroids, and the manual review process. An intramuscular (IM) injection is considered a single dose on the date IM injection is administered. This dose of corticosteroid will be referred to as “prednisone (or equivalent)” throughout this document.

Baseline prednisone (or equivalent) dose will be the total daily dose of all corticosteroids being taken by a patient on the day prior to the date of the first dose of study drug administration (baricitinib). This baseline dose will be used for baseline summaries and for comparisons to later visits. A daily dose of prednisone (or equivalent) will be calculated for each day between baseline and study discontinuation. The corticosteroid dose for a postbaseline visit will be the daily dose of prednisone (or equivalent) at each visit date minus 1.

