CLASI Activity Score	The proportion of patients with $\geq 50\%$ reduction from baseline in total activity score	Descriptive analysis with observed and NRI	mITT – patients with CLASI total activity score $\geq 10$ at baseline	Week 156 visit
SFI	Annualized severe flare rate	Descriptive analysis with observed rate	mITT	Week 0 to Week 156 visit
	Annualized severe flare rate	Descriptive analysis with observed rate	mITT	Week 0 to Week 156 visit
	Annualized severe flare rate	Descriptive analysis with observed rate	mITT	Week 0 to Week 156 visit
SLICC/ACR Damage Index Score	Change from baseline in SLICC/ACR Damage Index	Descriptive analysis with observed and mLOCF	mITT	Week 156 visit
LLDAS	Proportion of patients who achieve a LLDAS	Descriptive analysis with observed and NRI	mITT, patients with SLEDAI score of $\geq 4$ at baseline	Week 156 visit
Corticosteroid Sparing	Change from baseline in prednisone dose	MMRM	mITT	Week 156 visit
Worst Pain NRS	Change from baseline in Worst Pain NRS	MMRM	mITT	Week 156 visit
FACIT-Fatigue	Change from baseline in FACIT-Fatigue total score	MMRM	mITT	Week 156 visit
Worst Fatigue NRS	Change from baseline in Worst Fatigue NRS	MMRM	mITT	Week 156 visit
Worst Joint Pain	Change from baseline in Worst Joint Pain NRS	MMRM	mITT	Week 156 visit
Patient Global Impression of Severity	Change from baseline in Patient Global Impression of Severity	MMRM	mITT	Week 156 visit
SF-36 V2 acute	Change from baseline in mental component score (MCS)	MMRM	mITT	Week 156 visit
	Change from baseline in physical component score (PCS)	MMRM	mITT	Week 156 visit
	Change from baseline in domain scores SF-36 health survey version 2 acute	MMRM	mITT	Week 156 visit
EQ-5D-5L	Change from baseline in EQ-5D-5L US/UK population-based index scores and VAS.	MMRM	mITT	Week 156 visit
	Proportion of patients with no problem in each EQ-5D-5L item score	Descriptive analysis with observed and NRI	mITT	Week 156 visit

Measure	Variable	Analysis Method	Population	Key Time Point(s) a
WPAI-Lupus	Change from baseline in WPAI-Lupus	MMRM	For absenteeism score, presenteeism score, and work productivity loss score, population is a subset of mITT that includes patients who had an employment status of Yes at baseline. For activity impairment score, use mITT population	Week 156 visit

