### Corticosteroids

The following ATC codes will be used to select all possible systemic corticosteroids:

- H02 Corticosteroids for systemic use (except H02AA Mineralocorticoids), specifically
  - H02AB Glucocorticoids
  - H02BX Corticosteroids for systemic use, combinations
  - H02CA Anticorticosteroids,

and additionally

- M01BA Anti-inflammatory/antirheumatic agents in combination with corticosteroids

All unique preferred names in the database falling under the above ATC codes will be reviewed by the Lilly Medical Group in order to determine which ones should be included.

For each patient who has recurrent, intravenous injection of any corticosteroids with a start date or stop date during the treatment period (ie, from the date of randomization to the day of completion/early termination), the medications for this patient will be reviewed and the patient will be classified as having “prohibited” or “not prohibited” use during the treatment period.

Note: determination of prohibited use is based on a case-by-case assessment of recurrent intravenous corticosteroid use, considering if dose and/or duration of use are clinically relevant.

All corticosteroid doses need to be converted to prednisone equivalent doses. If additional conversion factors are required, these will be added to the table below in a SAP revision prior to database lock.

The following table should be used for converting nonprednisone medications to prednisone equivalent:

Multiply the dose of the corticosteroid taken by the patient (in milligrams) in Column 1 by the conversion factor in Column 2 to get the equivalent dose of prednisone (in milligrams).

*Example: Patient is taking 16 mg of methylprednisolone po daily. To convert to prednisone:  $16 \text{ mg methylprednisolone} \times 1.25 = 20 \text{ mg prednisone}$ . 16 mg of methylprednisolone po daily is equivalent to 20 mg of prednisone po daily.*

Column 1	Column 2
Corticosteroid Preferred Name	Conversion factor for converting to an equivalent prednisone dose
Prednisone	1
Prednisone acetate	1
Prednisolone	1
Prednisolone acetate	1
Prednisolone sodium phosphate	1
Methylprednisolone	1.25
Methylprednisolone acetate	1.25
Methylprednisolone sodium succinate	1.25
Triamcinolone	1.25
Triamcinolone acetonide	1.25
Triamcinolone hexacetonide	1.25
Cortisone	0.2
Cortisone acetate	0.2
Hydrocortisone	0.25
Hydrocortisone acetate	0.25
Hydrocortisone sodium succinate	0.25
Betamethasone	6.25
Betamethasone acetate	6.25

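### The prednisone-dose MMRM is censored at recurrent IV corticosteroid use classed as prohibited, so the steroid-sparing endpoint is censored on a form of its own outcome

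*SAP*

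**What the plan says.** **Endpoint.** The Corticosteroid Sparing row of SAP Table JAIM.6.4 is "Change from baseline in prednisone dose". It is analysed in the mITT population with Week 156 as the key time point, and MMRM is the only method listed.

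**What the dose counts.** SAP 6.10.1 says "Baseline prednisone (or equivalent) dose will be the total daily dose of all corticosteroids being taken by a patient". Postbaseline visit doses are prednisone-equivalent daily doses taken on the day before the visit. SAP 6.1 restricts steroid analyses to systemic products but does not exclude the intravenous route. The conversion table in SAP Appendix 1 includes the sodium succinate forms of methylprednisolone and hydrocortisone.

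**Censoring rule.** SAP 6.4.2.3 states that "any observed data after the date of the prohibited medication use will be excluded from the MMRM analysis" and adds: "The earliest date of prohibited medications will be used for censoring". It exempts no endpoint.

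**Trigger.** SAP 6.10 includes "recurrent intravenous injection of any corticosteroids" among prohibited medications, together with new antimalarials or immunosuppressants and with biologics or other protocol-prohibited products. Appendix 1 qualifies the steroid item: "determination of prohibited use is based on a case-by-case assessment of recurrent intravenous corticosteroid use", with dose and duration weighed for clinical relevance. Other steroid increases and tapering are permitted (Protocol 7.7, SAP 6.10) and stay in the model.

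**The concern.** The endpoint is meant to show how much corticosteroid patients needed over three years. Recurrent IV use judged clinically relevant is among the clearest signs that a patient needed more, and it is also the event that removes that patient's later doses from the model. A dose that was recorded is set aside and in effect replaced by a prediction.

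The SAP treats the same event differently elsewhere. Under the non-responder rule in SAP 6.4.2.2, prohibited medication counts as treatment failure for the visit interval. LLDAS, whose definition in Table JAIM.6.3 includes a prednisone-equivalent dose of at most 7.5 mg/day, would therefore score such a patient as a non-responder for that interval. The continuous steroid endpoint handles the event as ignorable missing data.

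At stake are the within-arm LS mean change, its 95% CI and its test against zero, which are the results that would answer the corticosteroid-sparing objective.

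**Working it through.** The plan gives no figure for this endpoint (no expected dose change, event rate or post-event dose), so there is nothing to reproduce.

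**Step 1: does the trigger overlap the outcome?** Yes. The outcome is the total systemic steroid dose (SAP 6.10.1), one trigger is a form of systemic steroid use (SAP 6.10), and the exclusion covers every MMRM (SAP 6.4.2.3).

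**Step 2: size in general form.** Let p be the share of an arm censored by the visit, D_after the mean dose recorded in those patients, and D_MAR the mean dose the model predicts for them. Then

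bias in mean change = −p × (D_after − D_MAR).

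Negative means towards sparing. The documents give none of the three inputs. For an assumed excess of 5 to 20 mg/day:

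- p = 1%: −0.01 × 5 = −0.05, to −0.01 × 20 = −0.20 mg/day
- p = 5%: −0.05 × 5 = −0.25, to −0.05 × 20 = −1.00 mg/day
- p = 10%: −0.10 × 5 = −0.50, to −0.10 × 20 = −2.00 mg/day

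**Step 3: can the repeated-measures model repair it?** A simulation used one arm of 1100 patients (the planned enrolment, used only for scale), the ten postbaseline visits and 60 runs per scenario. Assumed: baseline dose about 8 mg/day (SD 5, truncated at zero), residual SD 5, correlation 0.8 between adjacent visits, and an event risk that rises with the previous visit's dose. An unstructured likelihood fit to the censored data was compared with the mean of all doses taken.

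Bias at Week 156 in mg/day (sustained excess / excess fading by a factor e per 52 weeks):

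| Share censored | Excess −3 | Excess 0 | Excess 5 | Excess 10 | Excess 20 |
|---|---|---|---|---|---|
| about 2.5% | +0.06 / +0.02 | 0.00 / +0.01 | −0.13 / −0.03 | −0.25 / −0.08 | −0.49 / −0.14 |
| about 6% | +0.15 / +0.05 | −0.01 / 0.00 | −0.30 / −0.08 | −0.60 / −0.16 | −1.21 / −0.35 |
| about 12% | +0.29 / +0.08 | +0.01 / +0.01 | −0.58 / −0.16 | −1.17 / −0.32 | −2.35 / −0.63 |

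With about 6% censored and a sustained excess of 5, 10 or 20 mg/day, the change with all doses kept is −0.77, −0.48 or +0.14 mg/day. The censored model gives about −1.07 to −1.08 in all three.

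Three things follow:

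- The zero-excess column shows that the model adjusts properly for a dose already rising before the event. What it cannot recover is the excess after the event.
- A fading excess cuts the bias by roughly 70% to 75%.
- If later doses fall below the prediction, the sign reverses.

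**Step 4: what limits the size here.**

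- The visit dose is a single day's dose, and from Week 60 visits are 24 weeks apart. An infusion enters the outcome only if given on the day before a visit, so much of what is lost is the accompanying daily dose.
- Protocol 8.1.2 requires product to stop before a non-permitted agent that may be effective for SLE is introduced. That limits how much post-event dose data exist.
- SAP 6.10 derives the daily dose to treatment discontinuation and SAP 6.10.1 to study discontinuation, so the end of the usable dose record is not settled.

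**The case against.** **The hypothetical strategy is prespecified and uniform, so this is a choice of estimand.** In part. But the hypothetical trial in SAP 6.4.2.3 is one in which patients have complete data and stay on study treatment. It does not posit the absence of IV steroids. For an endpoint that measures steroid dose, removing steroid use removes part of the question.

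**MMRM uses each patient's own earlier doses, and patients with permitted increases stay in.** This stands, and the zero-excess results confirm it. It does not cover the excess after the event.

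**An observed analysis is already planned.** SAP 6.4 says both observed and imputed analyses will be done for efficacy measures, and SAP 6.4.2.1 promises observed summaries at each visit. A reader of Table JAIM.6.4 alone might infer that nothing besides the MMRM is planned, and the documents do not support that. Still, the table names an observed analysis in other rows and not in this one, and SAP 6.4.2.1 describes the strategy as conditional on completion and not causal.

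**Few post-event data may exist.** This stands as a limit on size. A reader might take Protocol 7.7 ("Any required corticosteroid bursts should be aligned with clinical practice") to show that censored patients generally continue on product. That sentence concerns permitted bursts, which do not trigger censoring. The SAP rule does, however, presuppose that some observed data follow prohibited use.

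**Other prohibited medication could act the other way.** This stands. Protocol 3.2 describes immunosuppressants as used to spare corticosteroids, so keeping doses after a new one could credit baricitinib with its effect. This is a reason for a narrow correction.

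**Conclusion.** The defect is in the current text: a form of high steroid use is both part of the outcome and a reason to discard the outcome. The bias is towards sparing where recorded doses after the event exceed the missing-at-random prediction. That is plausible, since the IV steroid counts in the dose, but the documents do not establish it. Over the assumed range of 2.5% to 12% censored with a sustained excess of 5 to 20 mg/day, it runs from 0.13 to 2.35 mg/day. It is roughly 70% to 75% smaller if the excess fades, about zero with no excess, and reversed if doses fall below prediction. All these inputs are assumptions.

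Three stronger readings are not supported:

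- That any repeated IV steroid use deletes data. Only use classed as prohibited on review does, and only later observations are lost.
- That every arm's estimate necessarily shifts towards sparing. The direction is conditional.
- That the bias is a known fraction of the reported effect. The documents give no expected mean change to divide by.

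This is one secondary endpoint with no planned between-arm comparison and no multiplicity-controlled claim. The correction is worth making because it is specific and cheap.

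**What to change.** 1. In SAP 6.4.2.3 and the Corticosteroid Sparing row of Table JAIM.6.4, state that the prednisone-dose endpoint is not censored when the prohibited medication is a corticosteroid, and that recorded prednisone-equivalent doses after that date are kept.
2. Keep the fully censored MMRM as a sensitivity analysis.
3. List the observed summary for this endpoint in the same row.
4. Censoring of this endpoint at new antimalarials, immunosuppressants or biologics may stay, since these could themselves lower the steroid dose. An uncensored version can be a further sensitivity analysis.
5. Reconcile SAP 6.10 and SAP 6.10.1 on whether the daily dose is derived to treatment or to study discontinuation.

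The cost is a sentence or two in the SAP, one amended table row and one further model run. The daily dose is already derived, so no new data are needed, and lifting the censoring recovers only doses that were collected. The downside is that the reported steroid reduction may look smaller.

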### 6.4.2.4. Modified Last Observation Carried Forward (mLOCF)

For patients who receive prohibited medication, the last nonmissing observation at or before prohibited use will be carried forward to that particular visit interval but not for the subsequent visit intervals (as defined in Section 6.4.2). For all other patients discontinuing from the study or permanently discontinuing the study treatment for any reason, the last nonmissing postbaseline observation on or before discontinuation will be carried forward to that particular visit interval but not for the subsequent visit intervals (as defined in Section 6.4.2). If a patient does not have a nonmissing observed record (or one imputed by other means) for a postbaseline visit, the last postbaseline record prior to the missed visit will be used for this postbaseline visit. If a patient does not have any postbaseline record at a scheduled, unscheduled or early termination visit, they will be excluded from the analysis.

## 6.5. Multicenter Studies

This study will be conducted at multiple sites internationally for each originating study. When specified, statistical analyses will adjust for geographical region. Classification of geographical region is defined in [Table JAIM.5.1](#).

## 6.6. Multiple Comparisons/Multiplicity

No adjustments for multiple comparisons will be utilized in the statistical analyses for this study.

## 6.7. Patient Disposition

Treatment and study disposition will be summarized for the modified intent-to-treat (mITT) population. Patient disposition will be summarized by treatment group with reasons for discontinuation. Included in the reasons for treatment or study discontinuation will be a category for discontinuations due to coronavirus disease 2019 (COVID-19)-related logistical issues (ie, quarantine or travel restrictions, non-illness related). For patients who discontinued the treatment or study due to COVID-19 infection, the reason for treatment discontinuation will be classified as “due to AEs” even when the discontinuation was due to the requirement of quarantine. Follow-up disposition will be summarized separately from the treatment period

summaries. A listing of patient disposition will be provided for all participating patients, with the extent of their participation in the study and the reason for discontinuation.

## 6.8. Patient Characteristics

Patient demographics and baseline characteristics will be summarized using the mITT population, by treatment group. No formal statistical comparisons will be made among treatment groups, unless otherwise stated. A listing of patient demographics will be provided.

## 6.9. Treatment Compliance

Patient compliance with investigational product will be assessed at each visit and at Early Termination during the treatment period by counting returned tablets. A patient will be considered significantly noncompliant if he or she misses more than 20% of the prescribed doses during the study, unless the patient's investigational product was withheld by the investigator for safety reasons. If a patient had his/her treatment temporarily interrupted by the investigator due to any reason, the number of days that drug was withheld or unavailable will be deducted from the total number of days in computing the expected total number of tablets used. Compliance for patients without available data due to early termination or lost-to follow-up will be based on last completed visit with available tablet count.

$$\text{Compliance} = \frac{\text{total number of tablets dispensed} - \text{total number of tablets returned}}{\text{expected number of total tablets}}$$

Patient treatment compliance will be summarized for the mITT population using the intervals defined in Section 6.4.2.

